Appendix E: Imputation Rules for Missing AE dates

Imputation rules for missing or partial AE start date are defined below. If the imputed AE start date is before the informed consent date, the AE start date will be imputed using the study informed consent date.

- **If only Day of AE start date is missing:**

- If the full (or partial) AE end date is NOT before the first dose date of the Treatment Period or AE end date is missing, then
 - if AE start year and month are equal to the month and year of first dose date of the Treatment Period, then impute the AE start day as the day of first dose date of the Treatment Period;
 - else if AE start year and month are equal to the month and year of first dose date of the Run-in Period, then impute the AE start day as the day of first dose date of the Run-in Period;
 - else impute the AE start day as 1.
- else if the full (or partial) AE end date is NOT before the first dose date of the Run-in Period, then
 - if AE start year and month are equal to the month and year of first dose date of the Run-in Period, then impute the AE start day as the day of first dose date of the Run-in Period;
 - else impute the AE start day as 1.
- else impute the AE start day as 1.

Compare the imputed AE start date with TE period to determine whether the AE is pretreatment AE, TEAE during the Run-in Period, TEAE during the Treatment Period, or post-treatment AE.

- **If Day and Month of AE start date are missing:**

- If the full (or partial) AE end date is NOT before the first dose date of the Treatment Period or AE end date is missing, then
 - if AE start year is equal to the year of first dose date of the Treatment Period, then impute the AE start month and day as the month and day of first dose date of the Treatment Period;
 - else if AE start year is equal to the year of first dose date of the Run-in Period, then impute the AE start month and day as the month and day of first dose date of the Run-in Period;
 - else impute the AE start month as January and day as 1.
- else if the full (or partial) AE end date is NOT before the first dose date of the Run-in Period, then
 - if AE start year is equal to the year of first dose date of the Run-in Period, then impute the AE start month and day as the month and day of first dose date of the Run-in Period;

- else impute the AE start month as January and day as 1.
- else impute the AE start month as January and day as 1.

Compare the imputed AE start date with TE period to determine whether the AE is pretreatment AE, TEAE during the Run-in Period, TEAE during the Treatment Period, or post-treatment AE.

- **If Year of AE start date is missing:**

If the year of AE start is missing or AE start date is completely missing then query site and

- If the full (or partial) AE end date is NOT before the first dose date of the Treatment Period or AE end date is missing, then impute the AE start date as the date of first dose date of the Treatment Period.
- else if the full (or partial) AE end date is NOT before the first dose date of the Run-in Period, then impute the AE start date as the date of first dose date of the Run-in Period.
- else impute AE date as the informed consent date.

The imputation should ensure the imputed AE start date is not before the informed consent date.

Imputation rules for partial AE end date are defined below:

If partial end date, then impute as min (the last day of the month, end of study participation) if day is missing, or min (Dec, end of study participation) if month is missing.

Appendix F: Criteria for Threshold Analysis

Table 12-3 Threshold Analysis Criteria for Laboratory Tests (as applicable)

Parameter	Threshold Analysis	Comments
Clinical Chemistry (LFT)		
ALT	>ULN - ≤3xULN >3x - ≤ 5xULN >5x - ≤ 8xULN >8x - ≤ 20.0xULN >20.0xULN	FDA DILI Guidance Jul 2009.
AST	>ULN - ≤3xULN >3x - ≤ 5xULN >5x - ≤ 8xULN >8x - ≤ 20.0xULN >20.0xULN	FDA DILI Guidance Jul 2009.
ALT or AST	(ALT>ULN - ≤ 3xULN) or (AST>ULN - ≤ 3xULN) (ALT>3x - ≤ 5xULN) or (AST>3x - ≤ 5xULN) (ALT>5x- ≤ 8xULN) or (AST>5x - ≤ 8xULN) (ALT>8x - ≤ 20xULN) or (AST>8x - ≤ 20xULN) ALT>20xULN or AST> 20 xULN	FDA DILI Guidance
Alkaline Phosphatase	>ULN - ≤ 1.5xULN >1.5 - ≤ 2.5 xULN >2.5 - ≤ 5.0 x ULN >5.0 - ≤ 20.0 x ULN >20.0 x ULN	FDA DILI Guidance Jul 2009.
Total Bilirubin	>ULN - ≤ 1.5xULN >1.5 - ≤ 2xULN >2 - ≤ 3xULN >3 - ≤ 10xULN >10xULN	FDA DILI Guidance Jul 2009.
Direct Bilirubin	>ULN - ≤ 1.5xULN >1.5 - ≤ 2xULN >2 - ≤ 3xULN >3 - ≤ 10xULN >10xULN	FDA DILI Guidance Jul 2009.
ALT and Total Bilirubin	ALT>3xULN and TBILI>2xULN	FDA DILI Guidance Jul 2009.
AST and Total Bilirubin	AST>3xULN and TBILI>2xULN	FDA DILI Guidance Jul 2009.
(ALT or AST) and Total Bilirubin	(ALT>3xULN or AST>3xULN) and TBILI>2xULN	FDA DILI Guidance Jul 2009.

Table 12-3 Threshold Analysis Criteria for Laboratory Tests (as applicable)

Parameter	Threshold Analysis	Comments
GGT	>ULN - ≤ 2.5xULN >2.5 - ≤ 5.0xULN >5.0 - ≤ 20.0xULN >20.0xULN	CTCAE grade 1-4
Clinical Chemistry (NON-LFT)		
Albumin	<LLN - ≥ 30 g/L <30 - ≥ 20 g/L <20 g/L	CTCAE grade 1-3
Amylase	>1x - ≤ 1.5xULN >1.5x - ≤ 2xULN >2x - ≤ 5xULN >5xULN	Criteria based upon CTCAE
Creatinine	>ULN - ≤ 1.5xULN >1.5 - ≤ 3.0xULN >3.0 - ≤ 6.0xULN >6.0xULN	CTCAE grades 1-4
Lipase	>ULN - ≤ 1.5xULN >1.5x - ≤ 2xULN >2x - ≤ 5xULN >5xULN	Criteria based upon CTCAE
Total protein	<LLN >ULN	No CTCAE
Creatine kinase	>ULN - ≤ 2.5 x ULN >2.5 - ≤ 5 x ULN >5 - ≤ 10x ULN >10 x ULN	CTCAE grades 1-4
Hematology		
Hemoglobin	Hgb decreased (anemia) <LLN - ≥ 100 g/L <100 - ≥ 80 g/L < 80 g/L	CTCAE grade 1-3
	Hgb increased >ULN - ≤ 20 g/L above ULN >20 g/L above ULN - ≤ 40 g/L above ULN >40 g/L above ULN	CTCAE grade 1-3
Platelets	Platelet decreased <LLN - ≥ 75.0 x 10e9 /L <75.0 - ≥ 50.0 x 10e9 /L <50.0 - ≥ 25.0 x 10e9 /L <25.0 x 10e9 /L	CTCAE grade 1-4
	Platelet increased >ULN	No CTCAE available

Table 12-3 Threshold Analysis Criteria for Laboratory Tests (as applicable)

Parameter	Threshold Analysis	Comments
Reticulocytes/Erythrocytes (%)	<LLN >ULN	No CTCAE
Coagulation		
Activated partial thromboplastin time (PTT)	>ULN - $\leq 1.5 \times$ ULN >1.5 - $\leq 2.5 \times$ ULN >2.5 x ULN	CTCAE grade 1-3
Prothrombin time (PT) International Normalized Ratio (INR)	>ULN - $\leq 1.5 \times$ ULN >1.5 - $\leq 2.5 \times$ ULN >2.5 x ULN	CTCAE grade 1-3

Table 12-4 Threshold Analysis Criteria for ECGs

Parameter	Threshold Analysis	Comments
HR	Bradycardia <50 bpm <45 bpm Decrease from baseline ≥ 10 bpm Decrease from baseline ≥ 20 bpm <50 bpm and decrease from baseline ≥ 10 bpm <50 bpm and decrease from baseline ≥ 20 bpm	Per HV grade 2, 3, plus shift change
	Tachycardia >100 bpm >115 bpm >130 bpm Increase from baseline ≥ 10 bpm Increase from baseline ≥ 20 bpm >100 bpm and increase from baseline ≥ 10 bpm >100 bpm and increase from baseline ≥ 20 bpm	Per HV grade 1, 2, 3, plus shift change
PR	≥ 240 ms ≥ 300 ms ≥ 200 ms and increase from baseline ≥ 40 ms ≥ 200 ms and increase from baseline ≥ 100 ms	
QRS	>110 ms >160 ms Increase from baseline ≥ 20 ms Increase from baseline ≥ 40 ms	

Table 12-4 Threshold Analysis Criteria for ECGs

Parameter	Threshold Analysis	Comments
QTc	>450 to <500ms (Male) or >470 to <500ms (Female) ≥500 ms	To be applied to any kind of QT correction formula.
	Increase from baseline Increase from baseline >10 ms Increase from baseline >20 ms Increase from baseline >40 ms Increase from baseline >60 ms	

Table 12-5 Threshold Analysis Criteria for Vital Signs

Parameter	Threshold Analysis	Comments
Pulse Rate	Same as above in ECG category	
SBP increased	>140 mmHg >160 mmHg >10 mmHg increase from baseline >20 mmHg increase from baseline	809/770 analyses
	>140 mmHg & >10 mmHg increase from baseline >140 mmHg & >20 mmHg increase from baseline >160 mmHg & >10 mmHg increase from baseline >160 mmHg & >20 mmHg increase from baseline	
SBP decrease	<90 mmHg <80 mmHg >10 mmHg decrease from baseline >20 mmHg decrease from baseline	Per HV grade 1, 3, plus shift change
	<90 mmHg and >10 mmHg decrease from baseline <90 mmHg and >20 mmHg decrease from baseline <80 mmHg and >10 mmHg decrease from baseline <80 mmHg and >20 mmHg decrease from baseline	

Table 12-5 Threshold Analysis Criteria for Vital Signs

Parameter	Threshold Analysis	Comments
DBP increased	>90 mmHg >100 mmHg >5 mmHg increase from baseline >10 mmHg increase from baseline	
	>90 mmHg and >5 mmHg increase from baseline >90 mmHg and >10 mmHg increase from baseline >100 mmHg and >5 mmHg increase from baseline >100 mmHg and >10 mmHg increase from baseline	
DBP decreased	<60 mmHg <45 mmHg >5 mmHg decrease from baseline >10 mmHg decrease from baseline	
	<60 mmHg and >5 mmHg decrease from baseline <60 mmHg and >10 mmHg decrease from baseline <45 mmHg and >5 mmHg decrease from baseline <45 mmHg and >10 mmHg decrease from baseline	
Weight	Weight gain ≥5 % increase from baseline ≥10 % increase from baseline ≥20% increase from baseline	CTCAE grade 1-3
	Weight loss ≥5 % decrease from baseline ≥10 % decrease from baseline ≥20% decrease from baseline	CTCAE grade 1-3

Table 12-6 Threshold Analysis Criteria for Laboratory Tests (for labeling purpose)

Parameter	Threshold Analysis	Comments
Clinical Chemistry (LFT)		
ALT or AST	>3xULN	For labeling purpose
	>5xULN	
	>8xULN	

Appendix G: Adverse Events of Special Interest

Table 12-7 MedDRA Preferred Terms for Event of Special Interest	
Adverse event of special interest	MedDRA preferred terms
Elevated transaminase	Alanine aminotransferase abnormal, Alanine aminotransferase increased, Aspartate aminotransferase abnormal, Aspartate aminotransferase increased, Transaminases abnormal, Transaminases increased, Liver function test abnormal, Liver function test increased, Hypertransaminasaemia, Hepatic enzyme abnormal, Hepatic enzyme increased
Rash	Rash, Rash erythematous, Rash macular, Rash maculo-papular, Rash maculovesicular, Rash vesicular, Rash pruritic, Rash follicular, Rash pustular, Rash generalized, Nodular rash, Drug eruption, Fixed eruption, Generalised erythema, Urticaria, Urticaria popular, Urticaria vesiculosa, Rash morbilliform, Rash popular, Rash papulosquamous, Rash rubelliform, Rash scarlatiniform , Drug hypersensitivity, Type IV hypersensitivity reaction, Dermatitis, Dermatitis atopic, Epidermolysis, Skin toxicity, Dermatitis allergic, Dermatitis exfoliative, Dermatitis exfoliative generalized, Erythema multiforme, Exfoliative rash, Mucocutaneous rash, Acute generalised exanthematous pustulosis, Cutaneous vasculitis, Urticarial vasculitis, Dermatitis bullous, Drug reaction with eosinophilia and systemic symptoms, Epidermal necrosis, Oculomucocutaneous syndrome, Skin exfoliation, Skin necrosis, Stevens-Johnson syndrome, Toxic epidermal necrolysis, Toxic skin eruption, Perioral dermatitis, Vasculitic rash

Note: the preferred terms listed in the table is based on the MedDRA version applicable at the time of finalization of the SAP. If the MedDRA version is upgraded at the time of the analysis, the corresponding preferred terms based on the upgraded version will be used in the analysis of adverse events of special interest.

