### **13.1.1.2 Clinically Significant Assessments**

Study assessments including laboratory tests, ECGs, PEs, and vital signs will be assessed and those deemed to have clinically-significant worsening from baseline will be documented as an AE. When possible, a clinical diagnosis for the study assessment will be provided, rather than the abnormal test result alone (e.g., urinary tract infection, anemia). In the absence of a diagnosis, the abnormal study assessment itself will be listed as the AE (e.g., bacteria in urine or decreased hemoglobin).

An abnormal study assessment is considered clinically significant if the subject has 1 or more of the following:

- Concomitant signs or symptoms related to the abnormal study assessment
- Further diagnostic testing or medical/surgical intervention
- A change in the dose of study drug or discontinuation from the study

Repeat testing to determine whether the result is abnormal, in the absence of any of the above criteria, does not necessarily meet clinically significant criteria. The determination of whether the study assessment results are clinically significant will be made by the investigator.

A laboratory value that is Grade 4 will not automatically be an SAE. A Grade 4 laboratory value will be an SAE if the subject's clinical status indicates a life-threatening AE.

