### **13.1.1.3 Documentation of Adverse Events**

All AEs will be collected from the time the ICF is signed until the subject completes study participation, as defined in [Section 9.1.7](#).

All subjects will be queried, using nonleading questions, about the occurrence of AEs at each study visit. When possible, a constellation of signs and/or symptoms will be identified as 1 overall event or diagnosis. All AEs for enrolled subjects will be recorded in the CRF and source document. AEs for subjects who are screened but not subsequently enrolled in the study will be recorded only in the subject's source documents. The following data will be documented for each AE:

- Description of the event
- Classification of "serious" or "nonserious"
- Date of first occurrence and date of resolution (if applicable)
- Severity
- Causal relationship to study drug(s)
- Action taken
- Outcome
- Concomitant medication or other treatment given

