9.4.7 Supportive Safety Analysis

9.4.7.1 Adverse Events of Special Interest

For this study, elevated transaminase events and rash events, as determined by MedDRA preferred terms in [Appendix G](#), are considered as adverse events of special interest.

For treatment-emergent elevated transaminase events and rash events, the following categories will be summarized by treatment group:

[figure not shown]
- Subjects with events
- Subjects with events by maximum severity
- Subjects with events leading to treatment discontinuation
- Subjects with events leading to treatment interruption
- Subjects with serious events
- Subjects with related serious events
- Subjects with events leading to death
- Duration of events
- Time-to-onset of first event

In addition, for treatment-emergent rash events, these categories will be summarized for the following subgroups:

- Sex (male, female)
- Female subjects with concomitant hormonal therapy (Yes, No)

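### The elevated-transaminase special-interest summary can miss elevations that are recorded under a hepatic diagnosis, because its term list holds only enzyme and liver-test terms

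*SAP*

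**What the plan says.** SAP 9.4.7.1 names two AESI categories, "elevated transaminase events and rash events, as determined by MedDRA preferred terms in" Appendix G. For each it plans counts by arm of subjects with events, maximum severity, discontinuation, interruption, serious, related serious and fatal events, plus duration and time to first onset. The section gives no laboratory criterion and no medical review step that could add a case.

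Table 12-7 in Appendix G lists the transaminase terms: "Alanine aminotransferase abnormal, Alanine aminotransferase increased, Aspartate aminotransferase abnormal, Aspartate aminotransferase increased, Transaminases abnormal, Transaminases increased, Liver function test abnormal", then "Liver function test increased, Hypertransaminasaemia, Hepatic enzyme abnormal, Hepatic enzyme increased". The rash row of the same table also contains diagnoses, among them toxic epidermal necrolysis and Stevens-Johnson syndrome.

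Protocol 13.1.1.2 sets the recording rule for abnormal assessments: "When possible, a clinical diagnosis for the study assessment will be provided, rather than the abnormal test result alone". The fallback is "In the absence of a diagnosis, the abnormal study assessment itself will be listed as the AE". Protocol 13.1.1.3 adds: "When possible, a constellation of signs and/or symptoms will be identified as 1 overall event or diagnosis". Protocol 13.1.2.2 has serious events recorded by a recognized medical term or a diagnosis.

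**The concern.** The two documents pull in different directions. The recording rule moves an event from the test result to the diagnosis whenever a diagnosis exists, while the AESI list recognises only the test result. A subject with a documented ALT or AST rise whose event is entered as, say, hepatitis or drug-induced liver injury matches none of the 11 terms.

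Protocol 9.8.1 requires a search for causes once an elevation meets an interruption criterion. It is reasonable to infer that such elevations are more likely than small ones to acquire a diagnosis, though the documents do not state this.

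The AESI summary is where a reader would look for seriousness, discontinuation, interruption, duration and onset of transaminase events taken together. It could show zero in a serious or discontinuation row although a diagnosed case with a documented elevation had occurred.

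**Working it through.** The plan states no figure on this point, so there is none to reproduce. The check is a comparison of texts, with simple arithmetic for scale.

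**1. The term list.** Table 12-7 has 11 transaminase terms. Ten end in abnormal or increased. The eleventh, Hypertransaminasaemia, is worded as a condition but means only raised transaminases. A search of the list for hepatitis, liver injury, hepatotoxicity, jaundice, hepatic failure, hepatocellular, cholestasis and bilirubin finds nothing.

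**2. Following one event through the rules.**
- Elevation, no diagnosis: the test result is the AE term (Protocol 13.1.1.2), it matches Table 12-7, and it is counted.
- Elevation with a diagnosis, and a listed term recorded as well: counted through the listed term.
- Elevation recorded only under a hepatic diagnosis: no match, not counted in any row of the AESI summary.

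Only the third path loses the event.

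**3. Where the third path is still visible.**
- SAP 9.4.1: TEAE tables by system organ class (SOC) and preferred term (PT), with separate tables for Grade 3/4, serious, related serious, discontinuation, interruption and death, and listings for these outcomes.
- SAP 9.4.2 and Appendix F: ALT and AST bands up to above 20 times ULN, the combination of ALT or AST above 3 times ULN with total bilirubin above 2 times ULN, the 3, 5 and 8 times ULN cut-offs in Table 12-6, and plots of maximum ALT and AST against maximum bilirubin. None of these depends on AE coding.

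These outputs do not pool transaminase events across terms, and they give no event duration or time to onset. Those appear only in the AESI summary.

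**4. Scale.** Inputs: 50 subjects per arm (Protocol 12.1). The number of true cases k and the share d recorded only under a diagnosis are assumptions, as the documents give neither.

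- One missed subject: 1/50 = 2.0 percentage points.
- Expected AESI rate = 100 × k × (1 − d)/50.

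| k (true rate) | d = 25% | d = 50% | d = 100% |
|---|---|---|---|
| 1 (2.0%) | 1.5% | 1.0% | 0.0% |
| 3 (6.0%) | 4.5% | 3.0% | 0.0% |
| 5 (10.0%) | 7.5% | 5.0% | 0.0% |

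**The case against.** The strongest defence is that the list fits its label. The category is elevated transaminase, not liver injury, and adding every hepatic diagnosis would change its scope. The rash row need not be a model, since rash is a clinical category and this one is a laboratory category. That stands against a broad widening of the list. It does not answer the case of a subject who did have an elevated transaminase and is left out only because of the term chosen.

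Second, the other outputs listed above already show these events and elevations, and the AESI summary sits under supportive safety analysis with no testing. This also stands, and it limits how much the point matters.

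Third, a reader might infer that the most serious liver events drop out of the table while mild ones stay. The documents do not support that. The recording rule applies only where a diagnosis is possible. Protocol 13.1.1.2 foresees that a Grade 4 laboratory value may be a serious event, so a large rise can be recorded under a laboratory term and counted as severe or serious. Protocol 13.1.2.2 allows a recognized medical term as well as a diagnosis. And discontinuation under Protocol 9.8.1 applies when no convincing alternative cause has been found, so those cases lack the viral, acetaminophen or alcohol explanation, although some might be recorded as drug-induced injury.

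Finally, the rash row contains evident misspellings: "Urticaria popular, Urticaria vesiculosa, Rash morbilliform, Rash popular". One might infer that rash events would be missed. That would require exact text matching, which the SAP does not specify. The spellings need an editorial correction only.

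**Conclusion.** The point holds as a possible undercount in one supportive, descriptive table. A transaminase elevation recorded only under a hepatic diagnosis is not counted in any row of the elevated-transaminase AESI summary. Each such subject lowers the arm's rate by 2.0 percentage points, assuming 50 subjects per arm in the Safety Set for the Treatment Period. The expected total cannot be derived, because the documents give neither a rate of liver events nor the share recorded as diagnoses. That larger elevations are more exposed is an inference from the cause investigation in Protocol 9.8.1. No event is lost from the report as a whole, and the primary and key secondary analyses are untouched. It is still worth correcting, because this is the only planned summary that pools these events and gives their duration and onset.

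**What to change.** Before database lock, amend SAP 9.4.7.1 and Table 12-7 so that the elevated-transaminase AESI also counts any TEAE coded to a hepatic diagnosis in a subject with treatment-emergent ALT or AST above 3 times ULN. Define hepatic diagnosis in advance, either as any preferred term in the hepatobiliary SOC or as a fixed list of hepatocellular-injury terms checked against the MedDRA version in use. Show these events separately from the laboratory-term events, so that the category as labelled stays readable. The laboratory condition keeps the category tied to raised transaminases and uses a threshold already derived for Table 12-6. Correct the rash spellings in the same amendment.

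The cost is a table edit and one extra derivation from data already collected. AESI counts may rise slightly. SAP section 4 already provides for amendment before lock, and making the change before unblinding avoids choosing terms after the results are known.
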